**Use of oral pregabalina as preemptive analgesia in abdominal
hysterectomy: evaluation of postoperative pain in a
randomized clinical trial.**

Register Clinical Trials (clinicaltrials.gov): NCT04495374

January, 20, 2021

METHODS

Study design

This study is revealed to be an experimental, randomized, double-blind, controlled placebo controlled clinical trial. The trial included only female patients, who would undergo abdominal hysterectomy surgery under spinal anesthesia, where after randomization as patients they were allocated into two groups, the placebo controlled group (P0) and the pregabalin 300 mg group (P1).

The entire study had been carried out a research protocol in accordance with the recommendations of the Consolidated Standards of Reporting Trials (CONSORT). The revised CONSORT statement in 2010, consists of a list of 25 items in a table that configure a checklist with guidelines for the development of randomized clinical trials with parallel groups, this statement also contains a flowchart to guide the experimental design of the study.

Study location and period

All procedures, procedures and data collections for this study were carried out at Santa Casa de Alfenas - MG (Casa de Caridade Nossa Senhora do Perpétuo Socorro). The inclusion of patients in the study and the collection of data from September 2019 to September 2020.

Sample population

Initially the sample size was out of base from a pilot study carried out with 10 patients, where establishing a 95% confidence level and a power above 80% using non-parametric tests (Mann-Whitney test) for primary study outcomes, to decide to make an initial allocation of 51 patients in each study group, totaling 102 patients. These 10 patients in the pilot study were also included in the final version of the study.

Prepared to an atypical health scenario issued by the pandemic of COVID-19, during the year of 2020, in the month of September of that same year to choose to carry out new statistical analyzes with a population included so far in the study. From these new analyzes, the results obtained were statistic for the primary outcomes and due to difficulties imposed by the pandemic caused by the coronavirus, it was decided to interrupt the data collection at this time, totaling a total of 55 patients included in the study.

The inclusion criteria are detailed below, where all are mandatory, and also the criteria and exclusion used to define the sample population.

Inclusion criteria: (1) Female patients; (2) Age between 20 and 65 years; (3) Patients who will undergo elective abdominal hysterectomy surgery due to benign pathologies; (4) Be classified as physical status by the Society of Anesthesiologists (ASA) as ASA I (healthy individual) or ASA II (patient with mild and controlled systemic disease);

Exclusion criteria: (1) Allergy or known intolerance to pregabalin or opioids; (2) Patients with chronic pain or fibromyalgia; (3) Patients on chronic use of opioids; (4) carriers of malignant neoplasms; (5) Pregnant women; (6) People with active uncontrolled cardiovascular disease; (7) Patients with kidney and / or liver disease; (8) Patients who have spinal deformities that make spinal anesthesia impossible; (9) Presence of coagulation disorders or anticoagulant therapy that cannot be suspended for surgery; (10) Presence of active sepsis;

After accepting to participate in the study and signing the informed consent form, the sociodemographic data of all patients were collected through a questionnaire, for further analysis.

Groups and interventions

As this is a randomized clinical trial, this study was made up of two groups. The group P0, the group designated as placebo controlled, and the group P1, consisted of patients participating in the intervention group.

Group P0: Received two placebo tablets composed of starch and aerosil (colloidal silicon dioxide).

Group P1: They received two tablets identical to the tablets in group P0, but in this case, the tablets were each composed of pregabalin in the 150mg dosage, totaling a total dosage of 300mg of pregabalin.

All tablets were made in the same pharmacy handling, under conditions provided for in good manufacturing practices, to avoid bias.

Blinding

In order to avoid measurement bias, after elaboration, the tablets were placed in opaque and sealed envelopes, being identified only as formula A or formula B. An external researcher, who was not involved in randomization or data collection, was responsible by blinding, being the only researcher to know the composition of each formula. At the end of the study, this researcher informed the rest of the team of the composition of each formula, with Formula A consisting of two tablets of 150 mg of pregabalin each, and Formula B consisting of two placebo tablets.

Since the patients included in the study, the researcher responsible for medication randomization and administration, and also the researcher responsible for monitoring and collecting data, did not have knowledge about the composition of the interventions (formula A and formula B).

Randomization

After determining the sample population and preparing interventions in sealed and opaque envelopes, the randomization procedure had been carried out. To carry out the random allocation process, an external researcher was responsible for administering to the patient a sealed, opaque envelope containing the intervention (placebo or pregabalin 300mg) over a period of 02 hours prior to the start of the anesthetic-surgical procedure, with randomization it was simple, carried out by entering the study, where the first patient to be admitted to the study received formula A intervention, and the second received formula B, and so on. Another researcher was responsible for the patient's perioperative follow-up and data collection.

Experimental draw

A total of 58 patients were selected for the research. After randomization, 30 patients were allocated to the P0 group (placebo), but during the follow-up two were excluded, one due to the use of subarachnoid morphine and the other due to the use of analgesic medications (tramadol) in the immediate postoperative period, which was not included in the study protocol. In the P1 group (pregabalin 300mg), 28 patients were allocated, in which one patient had to be excluded due to the use of subarachnoid morphine during anesthesia. Thus, the analyzes were performed with a total of 28 patients in the P0 group and a total of 27 patients in the P1 group.

Evaluation procedures and measures

After the patient inclusion process, blinding and random allocation to groups were carried out. The patients participating in the P0 group received a sealed envelope containing two placebo tablets, while patients belonging to the P1 group received an identical envelope containing two tablets of 150mg pregabalin each, all tablets were administered within two hours prior to the start of surgery. , in the nursing room where the patients were hospitalized.

In the operating room, venoclysis was performed with jelco No. 18 or No. 20, and an infusion of 08 ml.kg-1 of crystalloid solution (lactated ringer). The patients were properly monitored with pulse oximetry, cardioscope, and non-invasive blood pressure monitor. After monitoring, patients were premedicated with intravenous (IV) midazolam at a dosage of 0.03 mg.kg-1

To perform spinal anesthesia, the patients were seated on the surgical stretcher by the nursing team. Asepsis and antisepsis were performed at the puncture site with alcoholic chlorhexidine solution. After placement of sterile drapes, local anesthesia was performed with 2.0% lidocaine without vasoconstrictor. The first attempt at subarachnoid puncture was performed, using the median technique, between the intervertebral levels L3-L4 or L4-L5 or L5-S1, with a 25G Quincke needle for subarachnoid anesthesia. In case of technical difficulty in the puncture, the paramedian puncture technique was chosen. The confirmation of the correct puncture was based on the aspiration of cerebrospinal fluid. Anesthesia was performed with the local anesthetic 0.5% bupivacaine at a dosage of 0.3 mg.kg-1, injected from a 5 ml disposable syringe. After anesthesia, the patients were placed in the supine position, and the correct level of anesthesia was proven with thermal sensitivity tests using cotton soaked with alcoholic solution. After the anesthesia reached the sensory level of the T4 thoracic vertebra, the surgical team was allowed to start the procedure. Prior to the beginning of the surgical incision, a delayed bladder probe was performed in all patients according to the surgeon's indication. All surgeries were performed by the same team of surgeons.

Hemodynamic changes in blood pressure were controlled with the use of vasoactive medications such as ephedrine or metaraminol. For prophylaxis of postoperative nausea and vomiting (PONV) ondansetron was administered at a dosage of 4 mg intravenously (IV) 30 minutes before the end of surgery. It was prescribed for all

tenoxicam patients at a dosage of 20 mg IV at regular intervals every 12 hours for the purpose of anti-inflammatory and analgesic action. For analgesic relief, dipyrone IV was also prescribed at a dosage of 50 mg.kg⁻¹ at regular intervals every 6 hours. During the surgery, and also at the end of the surgery, the patients were evaluated for the degree of sedation using the Ramsay sedation scale as a basis.

At the end of the surgery, the patients were referred to the PACU, where they were monitored again, and went through the pain assessment process using the visual analog scale (VAS) in relation to pain at rest and “movement” (the patient was asked to perform the forced cough movement), through a direct question with scale demonstration. Pain characterized as mild (0 - 2 VAS) received no medication, in addition to those already prescribed; pain characterized as moderate (3 - 7 EVA) received IV morphine at a dosage of 0.025 mg.kg⁻¹; and severe pain (8 - 10 VAS) received IV morphine at a dosage of 0.05 mg.kg⁻¹ every 01 h until analgesic control. To be considered able to be discharged from the PACU for clinical follow-up in wards, patients should reach a score ≥ 9 on the modified Aldrete Scale (Table 3) and have VAS pain scores ≤ 2 .

Upon arriving at the infirmary, patients were periodically evaluated at regular intervals in relation to the intensity of pain, with the help of a team of properly trained and qualified nurses. For patients who presented moderate-intensity pain (VAS $\geq 2 < 8$) or pain classified as severe (VAS ≥ 8), IV morphine was administered at a dose of 1 mg and 2 mg, respectively, according to a medical prescription. All analgesic medications used were recorded in the patient's medical record. 24 h after discharge from the PACU, in the ward, the patient was evaluated by the same examiner who performed the evaluation in the PACU, who again performed the stratification of pain by VAS and an evaluation with the McGill questionnaire.

During the entire hospitalization period of the study patients, the use of CNS depressant drugs (example: ketamine, droperidol, promethazine) and / or analgesic drugs that are not included in the study protocol was avoided. If any of the patients were medicated with such drugs, they would be excluded from the study to avoid bias in the statistical analysis. The data related to surgery (pre, trans and postoperative) were collected for statistical analysis, according to Annex II, in which, for example, the total duration of surgery in minutes was described; the total of intravenous fluids infused; the values of mean arterial pressure and heart rate in the pre, intra and postoperative period;

the presence or not, as well as the quantity, of PONV in the PACU and after 24h; presence or not of dizziness as a possible side effect, among others.

Outcomes

The primary outcome was the assessment of postoperative pain using two different scales, the traditional visual analog scale (VAS) and the McGill Pain Questionnaire. The secondary outcome was the comparative analysis between the groups of opioid consumption in the postoperative period, evaluating both the total dosage of opioids used, as well as the time between the end of surgery and the request for the first analgesic rescue dose.

Other outcomes that were analyzed, apart from the variation in patients' hemodynamic data during the surgical times (pre, intra and immediate postoperative period), the degree of sedation was also evaluated using the Ramsay scale, and the presence of side effects such as nausea and vomiting, itching and dizziness. Other independent variables were analyzed, such as age, weight, body mass index, education level, profession, family income.

Ethical aspects and records

This study with the objective of preserving the patients' physical and psychological integrity followed the statements enunciated by the Declaration of Helsinki. All patients previously admitted to the study were clarified about the methodological process, the randomization and blinding process, the guarantee of confidentiality, about possible side effects of the interventions and also about the risks and benefits of participating in the study and the consent costs for participation in it. After clarifying any doubts and consenting to the patients' participation, the free and informed consent form (ICF) was signed, to which one of the copies was delivered to the patient and another copy was filed with the study researchers.

According to Resolution No. 466 of December 12, 2012, of the National Health Council, which addresses the guidelines and regulatory standards for research involving human beings, this study was approved by the Research Ethics Committee (CEP) of UNIFAL- MG under opinion number 3,334,050 on June 17, 2019 (ANNEX IV). This research was also recorded in the North American database for the registration of clinical trials, Clinical Trials (clinicaltrials.gov), under the protocol NCT04495374.

Statistical analysis

Descriptive analysis (median, mean and standard deviation) was performed for continuous variables that followed a standard distribution, and these were expressed in a table.

When analyzing parametric variables, the t test was used, and in comparisons between groups, the t test was used for independent samples, and in the analysis of data at different points in time between patients in the same group, we chose to use the test. t paired.

When evaluating non-parametric variables, the Mann-Whitney test was chosen. To compare numerical measurements between the times in each group, the Wilcoxon test was used for the related samples. To assess qualitative variables, Pearson's chi-square test or Fisher's exact test was chosen.

All data obtained were digitized and analyzed using the Statistic® 7.0 software, with a significance level of 5% ($p < 0.05$). For the elaboration of statistical graphs, the program used was the GraphPad Prism version 5.00 (Trial) of 2007.

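### Collection stopped at 55 analysed of 102 planned, after a look with no documented interim plan and partly because of the primary results, yet the primary tests keep an unadjusted p < 0.05

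*Combined protocol and SAP*

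**What the plan says.** The Sample population section bases the size on a 10-patient pilot, with 95% confidence, power above 80% and the Mann-Whitney test. This led the team "to decide to make an initial allocation of 51 patients in each study group, totaling 102 patients".

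The same section then describes the change of course. Against the background of COVID-19, the team decided, "in the month of September of that same year to choose to carry out new statistical analyzes with a population included so far", and gave two joint reasons for ending collection: "the results obtained were statistic for the primary outcomes and due to difficulties imposed by the pandemic". It reports 55 patients included.

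The Experimental draw section gives the fuller count: "A total of 58 patients were selected for the research", of whom 30 were allocated to placebo and 28 to pregabalin. Three were excluded after allocation, and "the analyzes were performed with a total of 28 patients in the P0 group and a total of 27 patients in the P1 group".

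The Outcomes section says: "The primary outcome was the assessment of postoperative pain using two different scales", namely the VAS and the McGill questionnaire. The Statistical analysis section runs its tests "with a significance level of 5" percent, with no adjustment. No section describes a planned interim analysis, a stopping boundary, a monitoring committee or a changed final threshold.

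**The concern.** A test at p < 0.05 has a 5% false-positive rate when the time of analysis does not depend on the result. Here the account itself names the primary results as one of two reasons for stopping. If a non-significant look would have been followed by more recruitment and a second test, a null treatment had two chances to reach p < 0.05, and the stated level understates the risk. If the pandemic would have ended collection in September 2020 whatever the data showed, there was one chance, and 5% is right.

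The trial's main conclusion rests on these primary tests, and a reader cannot tell which situation applies. A smaller matter is that the only power statement belongs to the 102-patient target and is not revisited for 28 v 27, so the document leaves the analysed sample without a stated power.

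**Working it through.** **Planned figure.** 51 × 2 = 102 is consistent, but the target cannot be rebuilt: no effect size, standard deviation or pilot result is given.

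**Counts.** 30 + 28 = 58 allocated; 58 − 3 = 55 = 28 + 27 analysed. So 58/102 = 56.9% of the target was allocated and 55/102 = 53.9% analysed.

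**Information fraction**, from n1·n2/(n1 + n2):
- Planned: 51 × 51/102 = 25.5.
- Analysed: 28 × 27/55 = 13.75, fraction 0.539.
- Allocated: 30 × 28/58 = 14.48, fraction 0.568.

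**Assumptions for the error rates.** Tests are two-sided at 0.05 (sidedness is not stated). There is no true effect. If the stopping condition was not met, collection goes on to 102 and a retest at 0.05.

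**One outcome drives the stop.** The two test statistics are bivariate normal with correlation √0.539 = 0.734. P(|Z1| > 1.96 or |Z2| > 1.96) = 0.0818, or about 0.081 at fraction 0.568. A direct Mann-Whitney simulation (200,000 null trials, 27 v 28 then 51 v 51) gives 0.0823.

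If continuation after a non-significant look had only probability q, the rate is 0.05 + q × (0.0818 − 0.05) = 0.05 + 0.0318q. It runs from 5% (q = 0) to 8.2% (q = 1).

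**Two primary scales**, error per outcome, 4 million simulated trials per row, fraction 0.539:

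| Correlation between scales | Stop only if both significant | Stop if either significant |
|---|---|---|
| 0 | 0.0516 | 0.0803 |
| 0.5 | 0.0555 | 0.0795 |
| 0.9 | 0.0677 | 0.0792 |

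Hand check at correlation 0. The chance that one outcome is significant at both looks is 0.05 + 0.05 − 0.0818 = 0.0182.
- Both required: 0.05 + 0.05² × (1 − 0.0182/0.05) = 0.05 + 0.0025 × 0.636 = 0.0516.
- Either suffices: 0.05 + 0.95 × (0.05 − 0.0182) = 0.0802.

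**Two-look benchmarks**, the nominal two-sided level at the first look that holds 5% overall:

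| Method | 55 analysed | 58 allocated |
|---|---|---|
| Pocock, constant boundary | 0.0299 | 0.0303 |
| Pocock-type spending | 0.0328 | 0.0341 |
| O'Brien-Fleming | 0.0069 | 0.0084 |
| O'Brien-Fleming-type spending | 0.0045 to 0.0076 | 0.0059 to 0.0093 |

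**The case against.** The strongest reply is that the pandemic explains both events. The Sample population section introduces the September 2020 analysis with COVID-19, so the pandemic appears to have prompted the look as well as being cited for the stop. The target, the look, both reasons and the final count are all disclosed. The plural wording about primary outcomes fits the both-scales rule better than the either-scale rule, and that rule gives the smaller inflation. All this stands, and it makes deliberate testing until significance less likely. It does not remove the point, because the result is still named as a reason and nothing says that collection would have ended without it. The stated collection period (September 2019 to September 2020) does not help either: the document is dated January 2021 and describes what happened.

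Some stronger readings are tempting but not supported:

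- **The true error rate is 8%.** That needs a continuation rule the text does not give. The Evaluation procedures section also has VAS at rest and on coughing in the PACU and VAS again at 24 h, besides McGill. Which of these counted as primary is not stated, so a two-outcome model is itself a simplification.
- **The pilot was a third look**, because "These 10 patients in the pilot study were also included in the final version of the study". The pilot is described only as the basis for the sample size. Nothing says it was tested between groups or could have stopped the trial.
- **A primary p-value above 0.030 fails.** The benchmarks run from about 0.005 to 0.033 by method, and none restores error control when the actual stopping rule is unknown.
- **The analysis had 53% power.** That assumes exactly 80% at 51 per group, with normal data. The text says above 80%, and 90% would give about 66%. Without an effect size no figure can be fixed.

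**Conclusion.** The point holds in conditional form. The document gives the primary results as a joint reason for stopping with 58 allocated and 55 analysed of 102 planned, documents no interim plan or boundary, and still applies an unadjusted 5% level. If the result influenced the stop, that level does not hold.

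The size depends on facts only the sponsor can supply. It is 5% if collection would have ended regardless, about 5.2% to 6.8% per outcome if both scales had to be significant, and about 8% if one outcome or either scale sufficed. The last two assume that collection would otherwise have gone on to 102. These are scenarios, not bounds. The reading of the garbled word as statistically significant is an interpretation, though the point needs only that the results were part of the reason. The missing explanation is certain; the amount of inflation is not.

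**What to change.** 1. **Sample population.** State that the September 2020 look was unplanned, or give the plan if there was one. State which primary measures informed the stop, and whether collection would have continued after a non-significant result.
2. **Statistical analysis.** Unless it can be shown that collection would have ended regardless, do not treat p < 0.05 alone as conclusive for the primary outcomes. Report each primary result with its effect estimate, confidence interval and exact p-value, and say that these p-values and intervals are not adjusted for the unplanned look. Two-look benchmarks (about 0.030 Pocock; about 0.005 to 0.008 O'Brien-Fleming type) may be shown for context, labelled as retrospective and method-dependent, with no fixed cut-off.
3. **Power.** State that the above-80% figure belonged to 102 patients and does not describe the 28 v 27 analysis. Insert no replacement figure.

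The cost is wording, plus estimates and intervals from existing data; no new patients are needed. The downside is that, unless the stop is shown to be independent of the result, a primary p-value just under 0.05 loses its unqualified claim of significance.

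### Blinding rests on two arm-wide letters given in order of entry, so if the pain assessor knew or inferred them, side effects building up under one letter could bias later pain scores

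*Combined protocol and SAP*

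**What the plan says.** The trial uses two codes. In the Blinding section, "the tablets were placed in opaque and sealed envelopes, being identified only as formula A or formula B", and the key is the same for every patient: "with Formula A consisting of two tablets of 150 mg of pregabalin each, and Formula B consisting of two placebo tablets". One external researcher held that key, "being the only researcher to know the composition of each formula", and disclosed it at the end of the study. Patients, the researcher who gave the medication and the researcher who collected data "did not have knowledge about the composition of the interventions (formula A and formula B".

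The Randomization section describes allocation by order of entry: "the first patient to be admitted to the study received formula A intervention, and the second received formula B, and so on". It separates giving the envelope from assessing the patient: "Another researcher was responsible for the patient's perioperative follow-up and data collection". The Experimental draw section reports 30 patients allocated to placebo and 28 to pregabalin.

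Under Evaluation procedures and measures, VAS is taken in the PACU by direct question with the scale shown. At 24 h after PACU discharge, "the patient was evaluated by the same examiner who performed the evaluation in the PACU", using VAS and the McGill questionnaire. The collected data also include "presence or not of dizziness as a possible side effect". Ramsay sedation is scored during and at the end of surgery, by an unnamed rater. The Outcomes section makes VAS and McGill the primary outcome.

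The plan describes no patient-specific code and no check of whether blinding held.

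**The concern.** Hiding what A and B contain is not the same as hiding which patients share a treatment. When one letter covers a whole arm, whatever an observer learns about one patient carries over to every other patient whose letter that observer knows, including patients without side effects. With patient-specific codes and an unpredictable sequence, it would not.

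What is at stake is the primary outcome. VAS and McGill are patient reports, but the examiner asks the question, shows the scale and records the answer, so prompting and expectation can enter. On the natural reading, the person who scores pain also records dizziness, and so sees both the clue to treatment and the outcome that the clue could influence.

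**Working it through.** **Step 1: what is hidden.** The Blinding section covers the composition of A and B. It does not say that the letter was kept from the data collector, and it does not say that the data collector saw it. Another researcher handed over the envelope.

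**Step 2: can the letter be inferred?** Strict alternation starting with A over 58 patients gives 58 / 2 = 29 A and 29 B. Under that rule B can never outnumber A. The reported counts are 28 A (pregabalin) and 30 B (placebo), so the rule was not followed exactly. The smallest departure that fits is one patient given B where A was due (29 − 1 = 28; 29 + 1 = 30). Entry order is therefore a strong but imperfect guide to the letter, and an opaque envelope does nothing against it.

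**Step 3: how much does a side effect reveal?** The documents give no side-effect rates, so the rates below are assumptions. Let pT and pC be the chances that a patient on pregabalin and on placebo shows a sign such as dizziness. Suppose the letters are known and, at the start, either is equally likely to be the drug.

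- One sign in one patient: P(that letter is the drug) = pT / (pT + pC). For 30% against 10%: 0.30 / 0.40 = 75%.
- After k patients per letter, choosing the letter with more signs and guessing on ties: P(correct) = P(X > Y) + ½ P(X = Y), with X ~ Bin(k, pT) and Y ~ Bin(k, pC).

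| pT / pC (assumed) | One sign | k = 5 | k = 10 | k = 14 | k = 28 |
|---|---|---|---|---|---|
| 20% / 10% | 66.7% | 65.9% | 72.9% | 76.8% | 85.3% |
| 30% / 10% | 75.0% | 77.9% | 87.0% | 91.0% | 97.3% |
| 40% / 10% | 80.0% | 86.5% | 94.5% | 97.2% | 99.7% |
| 40% / 20% | 66.7% | 75.1% | 83.5% | 87.7% | 95.1% |
| 50% / 30% | 62.5% | 73.7% | 81.9% | 86.0% | 93.8% |

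A guess without information is right 50% of the time. One sign raises a suspicion and no more; the pattern across patients is what identifies the letter.

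**Step 4: who would be affected.** Only assessments made after the guess. Ten patients per letter is 20 patients, leaving 58 − 20 = 38 allocated patients still to be assessed. Scores already recorded cannot change.

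The plan states no figure of its own on this point, so there is none to reproduce.

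**The case against.** The strongest objection is that the decisive link is not documented. No section puts the letter on the assessor's form or says the assessor saw the envelope, and the roles of giving and assessing are separate. This stands, and it makes the point conditional. It does not remove it, because the letter is not said to be hidden and entry order largely gives it away.

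Second, sedation and dizziness are non-specific here. Midazolam was given to all patients and morphine for moderate or severe pain. A reader might infer that one recognised reaction unmasks the trial; Step 3 does not support that. The Ramsay rater is also unnamed, so the argument rests on dizziness, which is listed among the collected data.

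Third, a reader might infer that one leak biases every patient's result, and that unique numbers alone would confine it to one patient. Neither follows. Earlier scores are fixed, and if entry-order allocation were kept, patients could still be linked through their order whatever number they carried.

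Fourth, seeing a letter of unknown meaning is not knowing the treatment. That is correct, and the double-blind label need not be withdrawn outright. It needs qualifying only if the assessor could see or infer the letters.

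**Conclusion.** The concern holds as a conditional design risk. Arm-wide letters combined with allocation by entry order mean that, if the pain assessor knew or inferred the letters, accumulating side effects could reveal an arm and bias the subjective primary outcome in patients assessed afterwards.

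Its size cannot be fixed from the documents. Over the assumed rates, the letter with more signs is the drug in 72.9% to 94.5% of cases after 10 patients per letter. These figures assume that letters are known without error; imperfect inference from entry order would weaken them. They measure how well the arm could be guessed, not how far VAS or McGill would shift.

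Two further assumptions apply: that the examiner who scores pain is the researcher who collects the side-effect data, and that pregabalin raises the rate of such signs above placebo. A reader might infer that the trial was in fact unblinded. Nothing in the documents shows that.

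**What to change.** **Design.** Label each envelope with a unique patient number drawn from a concealed random sequence, and put A or B on no envelope or form. The only list linking number to formula stays with the external researcher who already knows the composition. Numbering and the concealed sequence are both needed: numbers alone leave entry order as a link, and a random sequence alone leaves the shared letter.

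**Assessment order.** In the PACU and at 24 h, record VAS (and McGill at 24 h) before asking about dizziness and other side effects. This cannot apply to Ramsay scoring during surgery, which comes before any pain score.

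**This trial.** Collection has ended, so relabelling is no longer possible. The report should state whether the pain assessor could see or infer the letter. If so, it should give the shared code as a limitation and qualify the double-blind claim for the pain outcomes. It should also reconcile the 28/30 split with the stated alternation.

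**Cost.** Slightly more dispensing bookkeeping, with no extra staff or visits. The disclosure costs a few sentences.

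### Allocation is called simple randomization but described as A/B alternation by entry order, which gives 29/29 for 58 patients, not the reported 28 pregabalin and 30 placebo

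*Combined protocol and SAP*

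**What the plan says.** The Study design section calls the trial randomized and claims accordance with CONSORT. Groups and interventions repeats the label, and Evaluation procedures and measures says that "blinding and random allocation to groups were carried out".

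The Randomization section describes the method as follows: "with randomization it was simple, carried out by entering the study", and, in the same sentence, "the first patient to be admitted to the study received formula A intervention, and the second received formula B, and so on". No random-number source, sequence, block scheme or draw is described anywhere.

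The Blinding section gives the key disclosed at the end of the study: "Formula A consisting of two tablets of 150 mg of pregabalin each", with formula B as placebo.

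The Experimental draw section then gives the counts. "A total of 58 patients were selected for the research". For placebo, "30 patients were allocated to the P0 group (placebo"), "but during the follow-up two were excluded". "In the P1 group (pregabalin 300mg), 28 patients were allocated", of whom one was excluded. The analysis used 28 placebo and 27 pregabalin patients. The Sample population section adds that 10 pilot patients were carried into the final study. It does not say how they were allocated.

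**The concern.** Two conflicts appear within a few lines of each other. First, assigning the first entrant to A, the second to B and so on is alternation, not simple randomization. Second, alternation fixes the arm sizes exactly, and the reported arm sizes are different.

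The basis of the between-group comparison is at stake. If alternation was used, the next code follows from the order of entry, and opaque envelopes marked A or B do not hide it. Enrolment could then be influenced, and the word randomized would overstate the support for any causal conclusion. If a random sequence was used, the Randomization text misdescribes the trial's central safeguard, and how the sequence was generated is not reported. The current text cannot stand in either case.

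**Working it through.** **Inputs.** N = 58 selected; 30 allocated to placebo and 28 to pregabalin; exclusions 2 placebo and 1 pregabalin (all from Experimental draw). Rule A, B, A, B by entry, starting with A (Randomization). A = pregabalin, B = placebo (Blinding). Ten pilot patients included (Sample population).

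**Internal check of the counts.** 30 + 28 = 58; 30 − 2 = 28; 28 − 1 = 27; 28 + 27 = 55. These agree, so 30/28 is not an isolated typing slip, and the imbalance exists before exclusions.

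**Stated rule.** Alternation of N patients gives ⌈N/2⌉ of the first code and ⌊N/2⌋ of the second. For N = 58 this is 29 and 29. In an unbroken sequence starting with A, pregabalin minus placebo is only ever 0 or +1. The reported difference is 28 − 30 = −2, so the reported figure is not reproduced.

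**Could something simple explain the gap?**

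| Scenario | Pregabalin / placebo allocated | Matches 28/30? |
|---|---|---|
| Unbroken alternation of 58, either key | 29 / 29 | No |
| Pilot (10) and remainder (48) alternated separately, each starting with either code | 5/5 + 24/24 = 29 / 29 | No |
| Alternation over the 55 analysed, A = pregabalin, exclusions added back | 28 + 1 = 29 / 27 + 2 = 29 | No |
| Pilot not alternated and split 4/6, other 48 alternated | 4 + 24 = 28 / 6 + 24 = 30 | Yes, undocumented |
| One patient given B in place of A | 29 − 1 = 28 / 29 + 1 = 30 | Yes, undocumented |
| A = placebo, alternation over 55, each excluded patient replaced with the same formula | 27 + 1 = 28 / 28 + 2 = 30 | Yes, but contradicts the stated key and needs a replacement rule that is not in the text |
| True simple randomization of all 58 | any split | Yes, but contradicts the stated rule |

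**Probabilities, assuming 1:1 simple randomization.**
- Binomial(58, 0.5): P(exactly 28 on pregabalin) = 0.101; P(29/29) = 0.104; so P(any other split) = 1 − 0.104 = 0.896.
- Binomial(10, 0.5), for the pilot alone: P(4 on pregabalin) = 210/1024 = 0.205.

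The reported split is therefore ordinary under simple randomization and impossible under unbroken alternation of 58.

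**The case against.** The strongest reply is that the numerical gap is trivial. It is one patient per arm, a single wrong code would produce it, and it changes no analysis figure in the document. That is true as far as it goes. But alternation allows no tolerance, and the mismatch shows that at least one statement about allocation is wrong or incomplete. The conflict between label and rule also stands if the counts are set aside.

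A second reply is that the English is rough, so that simple may not be meant as the technical term and the closing words of the rule may be loose. This weakens the point about that one word. It does not remove the repeated claim of randomization. If the alternation wording is only loose translation, then the document gives no method of sequence generation at all, and the text still needs correcting.

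A third reply is that alternation may have been followed after all, with a misreported key and same-formula replacement of excluded patients. This reproduces every count, including the 55 analysed. Another possibility is uncounted entrants, for example 60 entered 30/30 with two pregabalin patients left out. Neither is documented, and the first contradicts the Blinding section. Both are fair warnings against reading the 28/30 split as evidence that a random sequence was used.

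Finally, the plan has real safeguards: sealed opaque envelopes, identical tablets, and a key withheld from the researchers who allocated and assessed. They limit how much bias should be inferred. They do not make an alternating sequence random, nor do they conceal which letter comes next.

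**Conclusion.** The concern holds. The label (simple randomization), the rule (alternation by entry, starting with pregabalin) and the counts (28 pregabalin, 30 placebo) cannot all be correct. The rule gives 29/29, so the discrepancy is one patient per arm. A reversed key alone does not remove it. The pilot patients could account for it only if they were not alternated.

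This rests on the plain reading of the rule as A, B, A, B and on 58 being the full number allocated. The documents do not show which statement is wrong. It is therefore conditional on the allocation records, not established here, that the trial was quasi-randomized. The correction is essential because it determines whether the comparison can be presented as randomized.

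**What to change.** 1. Check the allocation records of all 58 patients, including the 10 pilot patients, against the stated rule, the A/B key and the 30/28 counts. Correct whichever statement is wrong. State how the pilot patients were allocated and whether any excluded patient was replaced.
2. If alternation was used, replace the terms randomized and simple randomization with quasi-randomized allocation by alternation in order of entry, and limit any causal conclusion accordingly.
3. If a random sequence was used, describe how it was generated and delete the alternation text.
4. If the records cannot settle the matter, report the conflict as unresolved.
5. If the records show patients who received a code other than the one assigned, report this and analyse by assigned arm.

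The cost is a check of 58 allocation records and some rewording; no new data are needed. The downside is that the trial may no longer be presentable as fully randomized, or that the question stays open and must be reported as such.
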